### **Descriptive analyses**

Additional morbidity related outcomes will also be reported descriptively for the entire study population. Continuous variables will be reported as mean  $\pm$  standard deviation or median [interquartile range] as appropriate, while binary outcomes will be reported as N (%).

### **Sample size analysis**

This will be limited to the 85 patients expected to enroll in the SHARP study. Moerland et al found the a mean  $\pm$  SD of  $1.8 \pm 0.5$  in a healthy study population and  $2.9 \pm 1.4$  in a population with renal injury [M. Moerland, A. J. Kales, L. Schrier, M. G. J. van Dongen, D. Bradnock, and J. Burggraaf, "Evaluation of the EndoPAT as a Tool to Assess Endothelial Function," International Journal of Vascular Medicine, vol. 2012, Article ID 904141, 8 pages, 2012. doi:10.1155/2012/904141]. We expect similar variability in our cardiac surgery population. Assuming a conservative standard deviation of 1.4, we will have 90% power at the 0.05 significance level to detect an difference of 1.0 or greater in our study population. We will have 65% power to detect a clinically important difference of 0.73 (i.e., 25% of 2.9).

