## EXPERIMENTAL METHODS AND DATA ANALYSIS

### Research Design and Methods

This investigation will represent a substudy of a current ongoing clinical trial (SHARP: Voluven vs. Albumin comparing effect of 5% human albumin vs. 6% HES (130/0.4) on postoperative kidney function and coagulation. Patients who consent for SHARP study will be invited for participation in this substudy of endothelial/glycocalyceal function.

**Inclusion criteria:** Patients aged 40 – 85 years old who signed a written, informed consent for participation in this investigation, scheduled for elective aortic valve replacement with or without coronary artery bypass grafting involving nonpulsatile cardiopulmonary bypass, with or without additional minor surgical procedure.

**Exclusion criteria:** Patients with Raynaud's disease or other disease associated with upper extremity vascular insufficiency, and inability to perform EndoPAT exam (inability to lie still for 15 min, or significant finger deformity), patients meeting SHARP exclusion criteria (renal failure with oliguria or anuria not related to hypovolemia, dialysis, preoperative creatinine > 1.6 mg/dL, anticipated deep hypothermic circulatory arrest, known hypersensitivity or allergy to HES, clinical conditions with volume overload e.g., patients in pulmonary edema or congestive heart failure, severe hypernatremia or severe hyperchloremia, intracranial bleeding, pregnant or breast feeding women, critically ill adult patients e.g. patients who are hospitalized in the intensive care unit prior to surgery, severe liver disease, pre-existing coagulopathy).

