### **Statistical analysis**

Balance of randomized HES and albumin groups on potentially confounding baseline and procedural characteristics will be assessed using absolute standardized difference (ASD), defined as the absolute difference in means, mean ranks, or proportions divided by the pooled standard deviation. We define any variable with  $ASD > 0.25$  as imbalanced and will adjust for such variables in the following analyses. This substudy will be modified intent-to-treat, including all patients who enrolled in SHARP.

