### ***Primary analysis***

We will estimate the albumin effect on RHI using multivariable linear regression adjusting for imbalanced patient and procedure characteristics. Though we expect RHI to be normally distributed, appropriate transformations will be made if this is not the case (e.g., log transformation). If transformations are not successful, we will use nonparametric methods (i.e., Wilcoxon rank-sum test).

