### **Secondary analyses**

The albumin effect on each biomarker (i.e., syndecan 1 and endocan) at 1 hour and 24 hours after surgery will be assessed using separate repeated measures linear regression models adjusting for within-subject correlation, baseline biomarkers and imbalanced baseline variables. We will assess the heterogeneity of the treatment effect over time by testing the group-by-time interaction for each model using a criterion of  $P < 0.15$ . If heterogeneity is detected, we will analyze outcomes separately at each time, using additional Bonferroni correction as necessary. We expect that biomarkers will be lognormally distributed, so we will perform a log transformation and compare groups on ratio of geometric means. An alpha of 0.05 will be used for each set of the primary and sub/secondary analyses, with a significance criterion of 0.05 for the primary analysis and 0.0125 for each sub or secondary analysis (i.e., 0.05/4, Bonferroni). We will complete analyses using SAS version 9.4 or newer (SAS Institute, Cary, NC, USA) and R version 3.2.3 or newer (R Project for Statistical Computing, Vienna, Austria).

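### Does 65% power for the plan's own clinically important RHI difference, with no written rule for reading a non-significant result, call for a change?

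*Combined protocol and SAP*

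**What the plan says.** The Sample size analysis section takes its number from the parent trial: "This will be limited to the 85 patients expected to enroll in the SHARP study". It adopts an SD of 1.4, which it calls conservative, from a cited pair of results (1.8 ± 0.5 in healthy people, 2.9 ± 1.4 in renal injury). It states 90% power at the 0.05 level for a difference of 1.0, and then adds: "We will have 65% power to detect a clinically important difference of 0.73 (i.e., 25% of 2.9".

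The Primary analysis section says: "We will estimate the albumin effect on RHI using multivariable linear regression", adjusting for imbalanced characteristics. The Secondary analyses section gives the multiplicity scheme, "with a significance criterion of 0.05 for the primary analysis". No section mentions a confidence interval for RHI or compares the result with 0.73.

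On who is measured, Research Design and Methods says "This investigation will represent a substudy of a current ongoing clinical trial" and "Patients who consent for SHARP study will be invited for participation in this substudy of endothelial/glycocalyceal function". Its exclusions include "inability to perform EndoPAT exam (inability to lie still for 15 min, or significant finger deformity". The Statistical analysis section says: "This substudy will be modified intent-to-treat, including all patients who enrolled in SHARP".

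**The concern.** Three features together look like a weakness.

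- A plan that names a clinically important difference and reports 65% power for it accepts roughly a one-in-three chance of a non-significant result when that difference is real.
- The only criterion written down for the primary comparison is a P value. If a non-significant result were reported as no effect, an important benefit could be dismissed. An observed benefit of 0.50 and an observed 0.00 would both be non-significant, yet only the second rules out 0.73.
- The calculation uses all 85 parent-trial patients, while substudy participation is by invitation and patients who cannot have the tonometry examination are excluded. Fewer measurements would mean lower power than stated.

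The basis of 0.73 is also thin. It is 25% of a mean from a renal-injury group, and that mean exceeds the healthy one although the plan reads higher RHI as better function.

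**Working it through.** **Inputs.** From the Sample size analysis section: N = 85, SD = 1.4, differences 1.0 and 0.73 (0.25 × 2.9 = 0.725), significance level 0.05. Assumed because the plan does not state them: 1:1 allocation (42 and 43) and a two-sided test. One-sided testing would give 95% and 77%, which do not match the plan, so two-sided is the natural reading.

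**Stated power.** The standard error of the difference is 1.4 × √(1/42 + 1/43) = 0.304. With 83 degrees of freedom the critical t is 1.989. Power comes from the noncentral t distribution with noncentrality equal to difference / 0.304.

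| Difference | Noncentrality | Power | Plan |
|---|---|---|---|
| 1.0 | 3.29 | 90.2% | 90% |
| 0.73 | 2.40 | 66.1% | 65% |
| 0.725 | 2.39 | 65.5% | 65% |

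The plan's figures are right. The chance of missing a true 0.73 is about 34% (100% − 66.1%).

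**Fewer measured patients** (same method, SD 1.4). The plan gives no loss figure, so the smaller numbers are illustrative only.

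| N measured | Power for 0.73 | Power for 1.0 |
|---|---|---|
| 85 | 66.1% | 90.2% |
| 84 | 65.6% | 89.9% |
| 83 | 65.1% | 89.5% |
| 80 | 63.4% | 88.4% |
| 77 | 61.7% | 87.2% |
| 68 | 56.3% | 82.7% |
| 60 | 51.0% | 77.7% |

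The stated 65% survives the loss of two patients. Material erosion needs losses of 10% to 30% (77 down to 60 measured), for which the documents offer no basis.

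**What the interval would show.** The 95% half-width at N = 85 is 1.989 × 0.304 = 0.604.

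- Observed 0.50: interval −0.10 to 1.10, P = 0.10; 0.73 is inside.
- Observed 0.00: interval −0.60 to 0.60; 0.73 is excluded.
- In general, a non-significant observed benefit above 0.73 − 0.604 = 0.126 leaves 0.73 inside the interval.

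These readings need only the estimate and its standard error, both of which the planned regression produces.

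**Dependence on the SD.** At N = 85, power for 0.73 is 79% at SD 1.2, 91% at SD 1.0 and over 99% at SD 0.5. At SD 0.5 the half-width is 0.216, so a non-significant result has an upper limit of at most about 2 × 0.216 = 0.43 and always excludes 0.73. The difficulty is greatest at the SD the plan chose as conservative.

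**Could the number be raised?** 80% power for 0.73 at SD 1.4 needs 118 patients, 33 more than 85. The parent trial fixes the number, so that route is closed to the substudy.

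**The case for a change.** The best case for a change does not dispute the arithmetic. With the number fixed and power known to be modest, the proper response is to commit beforehand to a 95% interval and to call a non-significant result inconclusive when the interval contains 0.73. A rule fixed before the data are seen is worth more than one written afterwards, it costs a sentence or two, and the results are meant to support future grant applications. The ambiguous zone also does not need SD 1.4. Non-significant benefits of about 0.21 to 0.52 at SD 1.2, or 0.30 to 0.43 at SD 1.0, still leave 0.73 possible. And the invitation to parent-trial patients does not sit squarely with an analysis set of everyone enrolled in that trial.

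Much of this stands as good practice. No section names an interval, and the two statements on who is analysed could be worded alike. But the harm requires investigators to misread a non-significant estimate as no effect, and nothing in the plan directs them to. The primary analysis is framed as estimating the albumin effect. An analyst would report that estimate with its interval, and would analyse the patients who have an RHI measurement, as the word modified allows. Whether 85 is the parent trial's total or the number expected to take part cannot be settled from these documents. Questions about the 2.9 and 1.8 turn on a source not available here. A different justification for 0.73 would leave the test and the estimate as they are.

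**Conclusion.** No change is needed. The stated 90% and 65% are correct for 85 evaluable patients at SD 1.4, assuming equal arms and a two-sided test. The plan is candid that it is under-powered for its own important difference and that the parent trial limits its size, which is a fair trade-off for a substudy. The missing interval and reading rule are details that analysts fill sensibly from the planned regression, and following the plan as written gives no wrong result.

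The remaining exposure is one of interpretation. At SD 1.4 about 34% of trials with a true difference of 0.73 would be non-significant, and readers will need the interval, about ±0.60, to judge them. These figures are for an unadjusted comparison, so the adjusted analysis may differ somewhat. Naming the interval, stating that the powers assume 85 evaluable measurements, and aligning the wording on who is analysed would be useful clarifications in the report. None would change the primary test or its result.

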### **Project Timeline**

This project would take 2 years to complete. Institutional Review Board approval would require 2-3 weeks, followed by 1-2 weeks for training and certification of a Research Fellow in proper use of EndoPAT equipment by Itamar Medical representative. Patient enrollment is expected to be complete by January 2018, followed by additional 2-3 months for data interpretation and manuscript preparation.

## **OTHER SUPPORT**

### **Budget**

Total estimated expenses for this proposed research are \$25,000. These funds will be used to cover personell costs including 1.2 calendar months effort and 10% salary support for a trained Clinical Research Fellow and 0.6 calendar months effort and 5% salary support for an assigned Outcomes Research Department statistician. These funds will also cover cost of equipment including EndoPAT probes and labaratory blood testing for endocan and syndecan 1 levels. This project will not involve use of Clinical Research Unit, Lerner Cores, or Biostats.

### **Future investigation**

Perioperative endothelial dysfunction contributes to multi-organ system dysfunction after cardiac surgery. However, investigations examining perioperative endothelial dysfunction have been limited because of the inability to measure and quantify endothelial function. Use of peripheral arterial tonometry provides a unique and effective research tool to measure perioperative endothelial function which can be applied to numerous interventions. The measurement of perioperative biomarkers of endothelial injury

also characterize the consequence of perioperative inflammation in cardiac surgical patients and can be applied to future investigations. Our initial results will facilitate further analysis to determine the contribution of perioperative endothelial function to postoperative morbidity and mortality. Preliminary data gained from this investigation will be used to support future grant applications for investigation of new interventions on postoperative glycocalyx and endothelial damage measured by peripheral arterial tonometry and other molecular biomarkers. This proposed investigation and future investigations will contribute to our ultimate goal of improving early and long-term patient outcomes following cardiac surgery.

